9.5. Secondary Endpoints

Unemployment in the two years post-AA diagnosis will be identified using Read codes relating to unemployment recorded in the primary care record or the issuing of IB113 or ESA113 forms.

Time off work in the two years post-AA diagnosis will be indicated by the issuing of Med 3 certification from primary care (Statement of Fitness for Work certification).

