8. RESEARCH QUESTION AND OBJECTIVES

8.1. Study Objectives

The overall purpose of the study is to provide an estimate of the cumulative lifetime incidence of AA in the population overall and by sociodemographic groups (sex, ethnicity, deprivation, geographic location and urban-rural status). Moreover, to perform a subgroup analysis in the AA population to identify health-related disparities across people in different socioeconomic strata, geographical distribution, sex and ethnic groups. The disparities that will be considered are AA associated: Mental health conditions; healthcare utilisation; and work impact (time off work and unemployment).

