8.3. Secondary Objectives

8.3.1. Objective 4

Describe any disparities in AA related work impact (time off work and unemployment) across sociodemographic groups.

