9. RESEARCH METHODS

9.1. Study design

The study will use retrospectively collected anonymised data from all eligible patients in the Oxford-Royal College of General Practitioners (RCGP) Research and Surveillance Centre (RSC) dataset at the date of data extraction. The cohort to be used for this study has already been specified for previous work as follows:

All adults and adolescents (aged 12+) registered with practices contributing data to RCGP RCS between January 1, 2009 and December 31, 2018, will be eligible for inclusion in the study. People who have opted out of record sharing will not be included (approximately 1.8% of the adult population) and have not been uploaded to the RCGP RCS database. Cumulative lifetime incidence of AA will be estimated using cases of incident AA occurring during the observational study period (January 1, 2009 and December 31, 2018). For all analyses, the overall results including both adults

(aged 18+) and children (aged 12-17) will be published, with stratification by sex, ethnicity, deprivation quintile, geographic region and urban/rural classification.

The assessment of any associations with baseline characteristics and the outcomes of interest (objectives 2-4) will be assessed using Cox proportional hazards models (time to event outcomes) and Poisson regression (repeated event outcomes) models. Three different adjustment sets will be used for each endpoint analysis. These include: an unadjusted model, a sex and age adjusted model, and a multivariable model with an adjustment set of: body mass index (BMI), smoking status, alcohol use, and common comorbidities: type 2 diabetes, hypertension, atrial fibrillation, angina, acute myocardial infarction, stroke, heart failure, chronic liver disease, dementia, rheumatoid arthritis, asthma, chronic obstructive pulmonary disease, chronic kidney disease, malignancy and inflammatory bowel disease.

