9.1.1. Total disease burden; cumulative lifetime incidence

A cross-sectional design (incidence) will be used to assess the total disease burden of AA, stratified by sociodemographic groups.

9.1.2. Disparities in the impact of AA on mental health, work impact and healthcare utilisation

A matched-cohort design will be used for incidence of AA related: Mental health conditions; work impact; healthcare utilisation.

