Time off work for illness	Outcome	Defined using primary care codes for 'sick leave' or the issuing of a Med 3 certificate indicating time off work for illness
Unemployment	Outcome	Defined using primary care codes indicating unemployment or incapacity from work (IB113 [incapacity benefit] form or ESA113 form [Employment Support Allowance, which replaced IB113 from January 2011])
Body mass index	Potential confounder	Identified from primary care records using clinical codes.

Smoking status	Potential confounder	Identified from primary care records using clinical codes.
Alcohol use	Potential confounder	Identified from primary care records using clinical codes.
Type 2 diabetes	Potential confounder	Identified from primary care records using clinical codes.
Hypertension	Potential confounder	Identified from primary care records using clinical codes.
Atrial fibrillation	Potential confounder	Identified from primary care records using clinical codes.
Angina	Potential confounder	Identified from primary care records using clinical codes.
Acute myocardial infarction	Potential confounder	Identified from primary care records using clinical codes.
Stroke	Potential confounder	Identified from primary care records using clinical codes.
Heart failure	Potential confounder	Identified from primary care records using clinical codes.
Chronic liver disease	Potential confounder	Identified from primary care records using clinical codes.
Dementia	Potential confounder	Identified from primary care records using clinical codes.
Rheumatoid arthritis	Potential confounder	Identified from primary care records using clinical codes.
Asthma	Potential confounder	Identified from primary care records using clinical codes.
Chronic obstructive pulmonary disease	Potential confounder	Identified from primary care records using clinical codes.
Chronic kidney disease	Potential confounder	Identified from primary care records using clinical codes.
Malignancy	Potential confounder	Identified from primary care records using clinical codes.
Inflammatory bowel disease	Potential confounder	Identified from primary care records using clinical codes.

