9.4. Primary Endpoints

Objective 1: An incident diagnosis of AA is the date of the first diagnosis code in the record and no alternative diagnosis that merits exclusion (any form of scarring alopecia¹², traction alopecia, congenital alopecia, androgenetic alopecia, telogen effluvium, tinea capitis, trichotillomania, or secondary syphilis of the scalp) diagnosed in the subsequent 365 days from date of AA diagnosis.

Objective 2: Mental health condition outcomes will be assessed up to two years post-AA diagnosis and will comprise new onset depressive episodes, recurrent major depression, and anxiety disorders, defined by the International Statistical Classification of Diseases and Related Health Problems 10th Revision (ICD10) classification, and identified using algorithms validated for use in UK primary care data.

Objective 3: Healthcare utilisation outcomes will comprise primary care visits, dermatology referrals, referrals for psychological therapy (including those via IAPT; Improving Access to Psychological Therapies) and psychiatric reviews in the two years post AA diagnosis.

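### The Objective 4 endpoints do not require work loss to be new after AA, so work loss that began earlier can be counted as AA-related and can distort subgroup comparisons

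*Combined protocol and SAP*

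**What the plan says.** Objective 4 (section 8.3.1) is to "Describe any disparities in AA related work impact (time off work and unemployment) across sociodemographic groups". Section 8.1 describes the disparity work as a plan "to perform a subgroup analysis in the AA population to identify health-related disparities across people in different socioeconomic strata", which reads as a comparison among AA patients. Section 9.1.2 states a different frame: "A matched-cohort design will be used for incidence of AA related: Mental health conditions; work impact; healthcare utilisation".

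The endpoints are in section 9.5. For unemployment: "Unemployment in the two years post-AA diagnosis will be identified using Read codes relating to unemployment recorded in the primary care record", or by the issue of an IB113 or ESA113 form. For absence: "Time off work in the two years post-AA diagnosis will be indicated by the issuing of Med 3 certification from primary care". The variables table in section 9.3 describes unemployment as "Defined using primary care codes indicating unemployment or incapacity from work", which is a status and not a change of status.

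For mental health, by contrast, section 9.4 says that outcomes "will comprise new onset depressive episodes, recurrent major depression, and anxiety disorders".

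The exclusions in section 9.2.4 do not mention prior unemployment or sickness absence. Section 9.1 sets out three models: unadjusted, adjusted for age and sex, and "a multivariable model with an adjustment set of: body mass index (BMI), smoking status, alcohol use, and common comorbidities". None includes work status before AA. Section 9.11 says that subgroup disparities will be read on the assumption that outcomes are related to AA, and concedes that this cannot be confirmed for each work-impact event.

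**The concern.** Read literally, section 9.5 counts a record by its date alone. A person incapacitated for years before AA, for whom a form or code happens to be entered again in month 3, is an unemployment event. A person already on long-term sick notes has a time-off-work event at the next Med 3. Section 9.11 then has both interpreted as AA impact.

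What this does depends on the contrast, and the protocol points to two.

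- **Subgroups compared within AA patients (section 8.1).** Any difference in prior work loss between deprivation, ethnic or regional groups can pass into the Objective 4 result, even if AA affects work equally in all of them.
- **AA patients against matched comparators within each subgroup (section 9.1.2).** Carried-over records add to both arms and pull the ratio toward 1, more so where prior work loss is more common. AA could then appear to matter least in the group with the most prior work loss. The Cox and Poisson models in section 9.1 estimate ratios, so the planned output is on the affected scale.

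**Working it through.** **Is there a plan figure to reproduce?** No. The only calculation, in section 9.7.1, is confined to anxiety and depression. The documents give no rate of prior, carried-over or new work loss. Everything below is an illustration under assumed rates.

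**Model.** Let π be the share with work loss before AA, c the probability that this is recorded again in the two-year window, and q the risk of new work loss in the others. The risk under the endpoint as written is

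observed risk = πc + (1 − π)q.

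**Step 1: within AA patients, no true disparity.** Assume q is equal in two groups (true ratio 1.00), with π = 3% in the less deprived group and 10% in the more deprived. With c = 50% and q = 2%:

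- less deprived: 0.03 × 0.50 + 0.97 × 0.02 = 0.0150 + 0.0194 = 0.0344
- more deprived: 0.10 × 0.50 + 0.90 × 0.02 = 0.0500 + 0.0180 = 0.0680
- ratio: 0.0680 / 0.0344 = 1.98
- share of events that predate AA: 0.0150 / 0.0344 = 44% and 0.0500 / 0.0680 = 74%

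Range over c = 25% to 90% and q = 1% to 4%:

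| c | q | Less deprived | More deprived | Ratio |
|---|---|---|---|---|
| 25% | 4% | 0.0463 | 0.0610 | 1.32 |
| 50% | 2% | 0.0344 | 0.0680 | 1.98 |
| 90% | 1% | 0.0367 | 0.0990 | 2.70 |

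Over the same range, prior work loss makes up 16% to 74% of events in the less deprived group and 41% to 91% in the more deprived.

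**Step 2: equal prior work loss.** With π = 5% in both groups the two observed risks are identical, so the ratio is 1.00 for every c and q. The within-AA bias needs a difference in prior work loss (or in how often it is recorded again).

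**Step 3: AA against comparators.** Assume a true new-onset ratio of 1.5, q = 2% in comparators and 3% with AA, and the same π and c in both arms. With c = 50%:

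- π = 3%: (0.0150 + 0.97 × 0.03) / (0.0150 + 0.97 × 0.02) = 0.0441 / 0.0344 = 1.28; difference 0.97 points
- π = 10%: (0.0500 + 0.90 × 0.03) / (0.0500 + 0.90 × 0.02) = 0.0770 / 0.0680 = 1.13; difference 0.90 points

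Over c = 25% to 90% the ratio is 1.36 down to 1.21 at π = 3%, and 1.21 down to 1.08 at π = 10%. The term πc cancels from the difference, which equals (1 − π) × 1.00 point whatever c is. The absolute contrast is almost kept, while the ratios shrink unequally.

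**Step 4: restrict to people with no prior record.** If prior status is fully recorded, the risk is q. The within-AA ratio returns to 1.00, and the AA ratio to 1.5 in both groups.

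**The case against.** The strongest reply is that section 9.1.2 already applies the word incidence to work impact and names a matched-cohort design, so new events are the intent and background work loss is controlled for. The first part stands as intent: the gap is that 9.5 and 9.3 do not make it operational, since a first record after AA can simply be the next coding of an existing state. The second part stands on the difference scale, as step 3 shows, but not for ratios. The matching variables, ratio and comparator index date are also not given.

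Section 9.11 discloses that attribution is uncertain. That is fair, but it does not mention work loss before AA and offers no remedy. Cause cannot be read from the record; an earlier work-loss entry can be. Section 9.9 leaves detailed methods to an SAP whose text is not in the document reviewed. It may deal with prior status, but the endpoint rule itself is in the protocol.

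The contrast with Objective 2 should not be pressed far. The new-onset wording there precedes a list that includes recurrent depression, so its scope is unclear, and the Objective 3 endpoints carry no such rule either. Section 9.1 also plans Poisson models for repeated events without saying which outcomes they cover. If Med 3 issue is one, a first-ever rule would not be the natural choice for it.

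A reader might infer that Objective 4 will largely reproduce existing differences between groups. The documents do not support that. They give no work-loss rates and do not say how often codes or forms are re-entered. In the matched contrast the bias is also a different one: unequal dilution of ratios.

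**Conclusion.** The point holds as a gap in the endpoint definition. As written, sections 9.5 and 9.3 admit work loss that began before AA, nothing in the exclusions or adjustment sets removes it, and section 9.11 reads what is counted as AA-related. Objective 4 can therefore mix prior differences with change after AA.

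The direction depends on the contrast: a spurious group difference within AA patients, or ratios against comparators pulled unequally toward 1. The sizes in the working (within-AA ratios of 1.32 to 2.70 for a true 1.00; a true 1.5 read as 1.21 to 1.36 or 1.08 to 1.21) rest entirely on the assumed 3% and 10% prior work loss and the assumed c and q. They show what could happen and are not estimates for this cohort. This is a secondary, descriptive objective, but the correction is inexpensive and should be made before analysis.

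**What to change.** 1. **Unemployment (9.5 and 9.3).** Define the endpoint as a first unemployment code, IB113 or ESA113 record after index among people with none of these in their available pre-index record. Treat the codes and both forms as one set: section 9.3 notes that ESA113 replaced IB113 in January 2011, inside the study period, and a change of form should not read as new.
2. **Look-back.** State a minimum that the registration rule supports. Sections 9.2.1 and 9.2.4 assure only about six months of registration before AA. Use a two-year look-back as a sensitivity analysis.
3. **Already recorded at index.** Report these people separately by sociodemographic group.
4. **Time off work.** Add a pre-index Med 3 or sick-leave record (yes/no) as a covariate or stratum. Also reconcile 9.3, which counts sick-leave codes as well as Med 3, with 9.5, which names Med 3 only.
5. **Comparators.** Apply the same rules from their index date, including the minimum look-back.
6. **Reporting.** State which contrast answers Objective 4, and give absolute differences beside ratios by subgroup.

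The cost is protocol and SAP wording plus a look-back in records. Section 9.8 says that the study reuses an earlier extract, so the sponsor should confirm that it holds pre-index work codes. The at-risk group becomes somewhat smaller, and prior status will be misclassified for some people with a short earlier record. Adjusting for the pre-index period, or comparing with it, is a defensible alternative for unemployment if the restriction loses too many people.

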9.6. Data sources

The RCGP RSC is the longest running primary care network in the UK, collecting weekly data since 1964. The RCGP RSC database contains complete data on all events and clinical entities coded in UK primary care. These include demographic information, clinical diagnoses, laboratory test results, primary care issued prescriptions, process of care codes (e.g. specialist dermatology reviews), and anthropometric measurements (e.g. BMI), and are coded using the Read Coding system.¹⁵

9.7. Study size

9.7.1. Sample size calculations

A sample size calculation is only applicable to the incidence of mental health conditions of anxiety and depression in people diagnosed with AA.

Assuming 80% power, a 5% level of statistical significance and a background population prevalence of 15% for anxiety and 10% for depression,¹⁶ our anticipated sample size for AA (n = 6007) would be sufficient to detect a risk difference of 1.2% in depression between those with and without AA, and 1.5% difference in anxiety between those with and without AA. Sample size calculations were performed in OpenEpi,¹⁷ results are presented using methods of Kelsey.¹⁸

9.8. Data management

This study will utilise the previously extracted data from our previously published study.⁹ Individual patient data was anonymized at the point of data extraction. All data will remain in anonymized form and will be held on a secure server at the University of Oxford. The data will not be used for any purposes other than for the research which is described in the respective protocols and which has been approved by the RCGP RSC Research Committee. The sponsor, Pfizer Ltd, will not have access to the individual anonymised patient data.

All statistical analyses will be performed using R version 4.2.1.

9.9. Data analysis

Detailed methodology for summary and statistical analyses of data collected in this study will be documented in a statistical analysis plan (SAP), which will be dated, filed and maintained by the sponsor. The SAP may modify the plans outlined in the protocol; any major modifications of primary endpoint definitions or their analyses would be reflected in a protocol amendment.

9.10. Quality control

The sponsor delegates the conduct of this study to Momentum Data. The Momentum Data team will have full access to all the anonymized data in the study and all employees have completed information governance, information security, and data protection training provided by the University of Oxford and NHS (National Health Service) Digital. Data will be controlled in accordance with data protection legislation, protocols and policies of Momentum Data and NHS policies and processes, as defined in the NHS Data Security and Protection [DSP] toolkit for research and information governance. The research team at Momentum Data have extensive experience in working with routine healthcare data and have all completed relevant advanced degrees and have extensive experience using various large healthcare data sources from the UK including CPRD (Clinical Practice Research Datalink), The Health Improvement Network (THIN), RCGP RSC database, Optimum Patient Care Research Database (OPCRD), and others.

All codes lists utilised for data extraction will undergo the rigorous quality control process utilised by Momentum Data for multiple real world evidence studies. This process consists of manual code list generation by a coding expert with a clinical background. The list is then independently reviewed by a second coding expert. The lists then go through an automated quality control process to identify any potential formatting errors or coding inconsistencies. During the data extraction process, high frequency codes are independently reviewed by a third reviewer to ensure that the most commonly used codes correctly match the clinical entity they are being used to identify. A fourth quality control step may also be used to look for overlap between code or case definitions where multiple definitions are possible e.g., biochemical disease markers and clinical diagnosis codes for a condition. Finally once variables have been generated, the frequency and pattern of variable prevalence is compared with known data from previous analysis in other independent datasets and published literature. Any inconsistencies are reviewed and investigated as appropriate.

Statistical programming output is quality controlled by an independent statistical programmer. All final study outputs including tables and figures are subject to quality control review by two independent reviewers.

9.11. Limitations of the research methods

Disparities between sociodemographic subgroups will be interpreted based on the assumption of the primary/secondary outcomes being related to the AA. We have no definite way to identify that every occurrence of an outcome is related to AA in the context of healthcare utilisation and work impact outcomes.

This is an ecological study limited to the UK population and may not be generalisable to other populations.

We expect a substantial amount of missing data for the ethnicity variable which is a limitation of the dataset itself and could result in bias. Necessary sensitivity analyses will be undertaken to circumvent this and limit any impact this could have in our analysis.

We will perform additional exploratory analysis into the time between dermatology referral and dermatology review with the goal of potentially identifying NHS and private referrals and exploring regional differences. If this data is sufficient, based on provisional analysis, we will include additional study endpoints using this lag time between referral and dermatology review.

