7. RATIONALE AND BACKGROUND

Alopecia areata (AA) is a common, immune-mediated non-scarring form of alopecia. Our previous work has provided the most comprehensive analysis of the epidemiology of AA to date¹. This study demonstrated that the incidence of AA is 0.26 per 1,000 person-years in the UK (United Kingdom), with a peak incidence at age 25-29; however incident AA occurs across the lifespan. We found that AA is more common in people of lower socioeconomic status and in people from Black, Asian, and mixed ethnic groups compared to those of White ethnicity². However, these data formed a small component of the initial study and there is substantial scope to expand on these initial data to provide a greater understanding of the total disease burden across these groups including reporting lifetime risk estimates. Current lifetime risk estimates are taken from a single population-based study with just 530 AA cases in a single region of the United States (US)³ and most reported age, sex and ethnicity prevalence estimates that have been produced from studies performed in secondary care⁴⁻⁸. These studies are likely to be missing a large proportion of cases and therefore substantially underestimate the total disease burden in these groups.

Our previous work strongly suggested there are significant socioeconomic and ethnic disparities in healthcare and outcomes in people with AA. A comprehensive assessment of these potential disparities in AA is needed, this would strongly complement the existing work and support the use of newer therapies in AA.

Our previous work has also demonstrated that AA is associated with significant psychological consequences including an increased incidence of depression and anxiety⁹. These data suggest a socioeconomic gradient in the mental health impacts of AA (with AA associated with a greater mental health burden in those with lower socioeconomic status). However, the study was not designed to assess this as a primary outcome, and further analysis is required to fully understand these potential relationships.

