8.2. Primary Objectives

8.2.1. Objective 1

Describe the total burden of AA (cumulative lifetime incidence) across sociodemographic groups (including geographical distribution).

8.2.2. Objective 2

Describe any disparities in AA related mental health conditions across sociodemographic groups.

8.2.3. Objective 3

Describe any disparities in AA healthcare utilisation across sociodemographic groups.

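### Objective 2 does not say whether AA effects or AA-only outcomes are compared between groups, yet subgroup differences are to be read as AA-related by assumption

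*Combined protocol and SAP*

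**What the plan says.** Section 7 gives the reason for the mental health objective. Of earlier work it says: "These data suggest a socioeconomic gradient in the mental health impacts of AA". It adds that "the study was not designed to assess this as a primary outcome, and further analysis is required to fully understand these potential relationships". Objective 2 (section 8.2) is then: "Describe any disparities in AA related mental health conditions across sociodemographic groups".

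The analysis is described in two ways.

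- **Within AA patients.** Section 8.1 calls the disparity work a subgroup analysis in the AA population. Section 9.1 gives the only model statement for Objectives 2 to 4: "The assessment of any associations with baseline characteristics and the outcomes of interest (objectives 2-4) will be assessed using Cox proportional hazards models", with Poisson regression for repeated events and results stratified by sex, ethnicity, deprivation, region and urban/rural status.
- **AA against comparators.** The abstract (section 4) lists diagnosed AA as the exposure, section 9.1.2 names a matched cohort, and section 9.7.1 powers a comparison of people with and without AA.

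Section 9.4 sets the window: "Mental health condition outcomes will be assessed up to two years post-AA diagnosis". Section 9.3 refers to an index date but does not define it for comparators.

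Section 9.11 gives the rule of interpretation: "Disparities between sociodemographic subgroups will be interpreted based on the assumption of the primary/secondary outcomes being related to the AA". It then concedes that there is no sure way to know that "every occurrence of an outcome is related to AA in the context of healthcare utilisation and work impact outcomes". Mental health is not in that concession. Section 9.9 leaves detailed methods to a separate SAP, which is not among the documents reviewed.

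**The concern.** Depression and anxiety may vary with deprivation, sex, ethnicity and region in people who do not have AA. A difference between deprivation quintiles among AA patients therefore mixes two things: the background gradient, and any difference in what AA adds. Section 7 asks about the second. The model sentence in 9.1, applied to AA patients as 8.1 describes, estimates the mixture, and 9.11 says the mixture will be read as AA-related.

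At stake is a wrong conclusion under a primary objective: a background gradient published as a disparity caused by, or specific to, AA. The same applies less sharply to primary care visits, psychological and psychiatric care, and work outcomes. For healthcare, section 7 also says that "there are significant socioeconomic and ethnic disparities in healthcare and outcomes in people with AA", so a within-AA description answers part of Objective 3 as posed.

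**Working it through.** **1. The plan's own figure.** Inputs from 9.7.1: 6,007 AA cases, 80% power, 5% significance (two-sided assumed), background 10% for depression and 15% for anxiety, Kelsey method. The matching ratio r is not stated. Kelsey: n = (1.960 + 0.842)² × p̄(1 − p̄)(r + 1) / (r d²), where p̄ is the weighted mean risk. Solving for d at n = 6,007:

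| Comparators per case | Depression (points) | Anxiety (points) |
|---|---|---|
| 1 | 1.59 | 1.87 |
| 3 | 1.27 | 1.51 |
| 3.5 | 1.24 | 1.48 |
| 4 | 1.23 | 1.45 |
| 5 | 1.20 | 1.42 |

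The stated 1.2 and 1.5 points both follow at about 4:1. They are sound for AA against no AA overall, which is not a between-group contrast.

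**2. AA-only comparison when AA has no effect.** Assumptions, not protocol figures: equal quintiles (6,007 / 5 ≈ 1,201 cases each); the 9.7.1 prevalences as least-deprived two-year risk; a crude comparison; background gradient g between extreme quintiles. Power = Φ(difference / SE − 1.96), SE = √[p₁(1 − p₁)/1,201 + p₂(1 − p₂)/1,201].

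- 10% v 12.5% (g = 1.25): SE 1.288 points, z = 2.5/1.288 = 1.94, power 0.49.
- 15% v 18.75% (g = 1.25): SE 1.526, z = 2.46, power 0.69.
- 10% v 15% (g = 1.5): SE 1.346, z = 3.72, power 0.96.
- 15% v 22.5% (g = 1.5): SE 1.585, z = 4.73, power 0.997.

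Range: at g = 1.1 the figures are about 13%/17%. With a 5% baseline they are 0.265 (g = 1.25) and 0.717 (g = 1.5). With unequal extreme quintiles of 601 and 1,802 cases they are 0.41/0.59 (g = 1.25) and 0.92/0.99 (g = 1.5).

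These are powers to see a gradient that really exists among AA patients. They become errors only when the gradient is read as AA-related. In 20,000 simulated studies on the same assumptions with 4:1 comparators, AA-by-quintile tests rejected in 4.6% to 5.3%.

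**3. Scale.** Suppose AA multiplies risk by 1.3 in every quintile and background risk rises from 10% to 15%. AA risks are 13.0% and 19.5%, an AA-only difference of 6.5 points. Of that, 5.0 is background and (19.5 − 15.0) − (13.0 − 10.0) = 1.5 is a difference in risk differences. The ratio of risk ratios is 1.00. The answer depends on a scale that the protocol does not name.

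**4. Detectable difference between groups (80% power, 4:1, equal quintiles).** For extreme quintiles with background variance in every cell, SE = √[2 × p(1 − p)/1,201 × (1 + 1/4)] = 1.369 points for depression and 1.629 for anxiety. Multiplying by 2.802 gives 3.83 and 4.56. Using the raised risk in the affected AA cell gives 4.09 and 4.78; adding a background gradient of 1.25 gives 4.27 and 4.97. A linear trend over five quintiles, expressed end to end, has SE = 4 × √[p(1 − p) × 1.25/(1,201 × 10)] = 1.224 and 1.457, hence 3.43 and 4.08 (3.64 and 4.26 with effect variance). The range is about 3.4 to 4.3 points for depression and 4.1 to 5.0 for anxiety. Power for a between-quintile difference as small as 1.2/1.5 points is about 14%/15%. None of this allows for correlation within matched sets.

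**The case against.** The strongest reply is that the protocol does contain the right design. AA is the listed exposure, a matched cohort is named, sociodemographic factors are subgroup variables, and the power statement compares people with and without AA. Stratum-specific AA effects could follow directly. The objective says only that disparities will be described, the detail belongs in an SAP not seen here, and 9.11 discloses its assumption openly. The illustrative gradients are assumed, and the planned age-sex and multivariable models could change the crude figures.

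Much of this stands. A reader might infer that no comparison of AA effects is planned, or that the study will certainly misattribute a background gradient. The documents do not support either: they are ambiguous, and the SAP may settle the matter. Nor is the 9.7.1 figure wrong, and no formal test of effect modification is promised.

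Three things remain. A description labelled AA-related still needs each group's non-AA background. Having comparators is not the same as stating how AA effects are compared between strata. And the rule in 9.11 is protocol text: disclosing an assumption does not make it harmless when the named cohort could check it, and its explicit caveat leaves out the mental health outcomes.

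**Conclusion.** The concern holds as an ambiguity joined to an unsafe rule of interpretation. Sections 8.1 and 9.1 point to AA-only associations; the abstract, 9.1.2 and 9.7.1 point to AA against matched comparators. The between-group contrast is unstated in the supplied documents, and 9.11 would attribute what is found to AA.

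The harm is conditional on the AA-only reading. Under the assumptions in step 2 of the working, a background gradient of 1.25 would then yield a significant apparent AA disparity about half to two-thirds of the time, and a gradient of 1.5 nearly always. The direction does not depend on those inputs; the percentages do. It should be settled before analysis because it governs what a primary objective can conclude.

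**What to change.** 1. **Section 9.1.** Reconcile 8.1 and 9.1 with 9.1.2. For mental health outcomes, and for general healthcare use and work outcomes where attribution to AA is intended, fit the planned Cox and Poisson models in AA cases plus matched comparators. Set each comparator's index date to the matched case's diagnosis date. Include AA-by-factor terms for each stratification factor, and report stratum-specific AA effects and between-stratum contrasts with 95% confidence intervals. Make AA-by-deprivation on the Objective 2 outcomes the main contrast, since section 7 describes a socioeconomic gradient.
2. **Within-AA comparisons.** Keep them, for example for dermatology referrals, labelled as descriptive and not attributable to AA.
3. **Section 9.11.** Replace the attribution assumption and extend the non-attribution caveat to mental health.
4. **Section 9.7.1.** Keep 1.2/1.5 points as overall AA against no AA and state the matching ratio. Add that, with equal quintiles and 4:1 matching, between-quintile differences in AA effect below roughly 3.4–4.3 points (depression) or 4.1–5.0 points (anxiety) would not be detected with 80% power, so a null contrast is not evidence of no disparity.

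Multiplicity adjustment, trend or joint test, and the primary scale are choices for the sponsor's SAP.

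Cost: protocol wording and model specification, with no new data. Intervals will be wider. Terms to report come to 21 per outcome if age is included: deprivation 4, region 8, ethnicity about 4 (assuming five groups), sex 1, urban/rural 1, age 3. Small strata will support estimation only.
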